**5.4. Data to be collected, including long-term follow-up data:**

Outcome data are self-report and will be collected online using the study website (Table 5). All measures have evidence of reliability and validity in youth in this age range, and include the core measures recommended for pain clinical trials. T1 = pre-treatment; T2 = post-treatment (2 months); T3 = follow-up (6 months post-treatment).

**6. Data and Specimen Banking**

**6.1. Complete list of the data and/or specimens to be included in the bank:**

N/A

**6.2. Location of data and/or specimen storage:**

N/A

**6.3. List of those with direct access to data and/or specimens in the bank:**

N/A

**6.4.** Length of time data and/or specimens will be stored in the bank:

N/A

**6.5.** Procedures for protecting the confidentiality and privacy of the subjects from whom the data and/or specimens were collected.

N/A

**6.6.** How the data and/or specimens will be made available for future use:

N/A

**6.6.1.** Who can request data and/or specimens from the bank:

N/A

**6.6.2.** Format in which data and/or specimens will be provided:

N/A

**6.6.3.** Process for investigators to request data and/or specimens.

N/A

**6.6.4.** Restrictions on future use:

N/A

**6.6.5.** Plan for providing data results from banked data/specimens:

N/A

**7. Sharing of Results**

**7.1.** Plan to share results with subjects/others:

If requested by the participant, study results will be shared with participants after participation is complete and findings are published. These results would be in the form of a letter outlining study findings.

**8. Study Timelines**

**8.1.** Duration of an individual subject's participation in the study:

Subjects will be participating in the study for approximately 10 months.

**8.2.** Duration anticipated to enroll all study subjects:

Approximately 3.5 years.

**8.3.** Estimated date for the investigators to complete this study:

We estimate that December 2022 will be the final data collection date for primary outcome measure and will be conducting data analysis for another 1-2 years.

**9. Study Population**

**9.1.** Inclusion criteria for each subject population (e.g., patients, parents, providers):

**Inclusion Criteria:** Youth will be eligible if they (a) are aged between 12-18 years, (b) are diagnosed with any type of SCD, (c) are able to speak and read English, (d) score at least 4 on

the Sickle Cell Pain Burden Interview (SCPBI), and (e) have access to the internet on a smartphone. Parents or caregivers will be eligible if they (a) are able to speak and read English and (b) have access to the internet on a smartphone or computer.

**9.2. Exclusion criteria for each subject population:**

**Exclusion Criteria:** Youth will be excluded if they have significant cognitive limitations that would impair their ability to use and understand the *iCanCope with Sickle Cell Pain* program, as per their healthcare provider or parent. Youth will also be excluded if they have previously received more than 4 sessions of outpatient psychological therapy for pain management in the 6 months prior to the time of screening.

**9.3. Vulnerable populations involved in the study:**

Children/Teenagers

Risk assessment specific to this vulnerable population and additional safeguards:

The research is considered minimal risk as the probability and magnitude of psychological and physical risks anticipated in this research are not greater than those ordinarily encountered in daily life or during the performance of routine physical or psychological examinations or tests. The relaxation skills and pain coping strategies taught in the online program is comparable to what is taught within clinical programs. The participant has the option of withdrawing participation at any time during the study. Knowledge gained through this research will guide future research and interventions to help adolescents with SCD.

Children who are Wards of the State

Risk assessment specific to this vulnerable population and additional safeguards:

[Click here to enter text.](#)

Adults Unable to Consent

Risk assessment specific to this vulnerable population and additional safeguards:

[Click here to enter text.](#)

Neonates of Uncertain Viability or Non–Viable Neonates

Risk assessment specific to this vulnerable population and additional safeguards:

[Click here to enter text.](#)

Pregnant Women

Additional safeguards:

[Click here to enter text.](#)

Prisoners

Additional safeguards:

[Click here to enter text.](#)

**10. Number of Subjects**

**10.1. Total number of subjects to be enrolled locally:**

60 dyads: children with SCD and their parents will be enrolled from Seattle Children's Hospital.

**10.2. Total number of subjects to be enrolled across all participating sites:**

160 dyads: children with SCD and their parents will be enrolled from participating sites.

**10.3. Number of screened subjects versus the actual number enrolled in the research:**

Participants will be recruited from pediatric centers with SCD patient populations. The patient populations at these centers provide access to about 500 patients who are likely eligible for recruitment into this study based on proposed inclusion criteria. We anticipate a 30-40% refusal rate based on our experience recruiting in this population.

**10.4. Power analysis:**

Based on prior and current study experience, and the pool of available study candidates, we plan to enroll a total of 160 subjects into the pilot RCT. With attrition conservatively estimated at 20% we expect a final sample size of 128. This proposed sample size is based on the following power calculation using preliminary data from investigator experience with prior pain trials and published trials in SCD:

Calculations are based on expected differences in youth pain-related disability and pain intensity. Group sample sizes of 52 and 52 achieve 84% power to detect a difference of 1.0 in pain-related disability between the two treatment conditions, with three assessments, AR(1) covariance structure, SD=4, ICC=0.2, and alpha=0.05. If the difference is 1.5 between treatment arms, then 52 per group achieves 99% power with the same assumptions. For pain intensity, group sample sizes of 49 and 49 achieve 80% power to detect a difference of 0.75 in pain intensity (average over three time points) in a design with 3 repeated measurements having a AR(1) covariance structure, SD=2, ICC=0.2 and 0.05 alpha.

**11. Withdrawal of Subjects****11.1. Anticipated circumstances under which subjects will be withdrawn from the research without their consent:**

The PI may decide to withdraw participants from the study if a family is not able to comply with study procedures or do not understand study instructions.

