### **3. Study Endpoints**

#### **3.1. Primary and secondary endpoints:**

Primary endpoint is greater reductions in pain-related disability. Secondary endpoint is the reduction of pain and anxiety/depressive symptoms.

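### The 84% and 99% power stated for pain-related disability do not follow from the stated inputs, which give about 49% and 83%

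*Combined protocol and SAP*

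**What the plan says.** Section 3.1 sets the endpoint: "Primary endpoint is greater reductions in pain-related disability". Section 10.4 then gives two power calculations as the basis for enrolling 160.

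- **Disability.** "Group sample sizes of 52 and 52 achieve 84% power to detect a difference of 1.0 in pain-related disability between the two treatment conditions". This result is said to hold under the following assumptions: "with three assessments, AR(1) covariance structure, SD=4, ICC=0.2, and alpha=0.05". A second scenario follows: "If the difference is 1.5 between treatment arms, then 52 per group achieves 99% power with the same assumptions".
- **Pain intensity.** 49 per group are said to give 80% power for a difference of 0.75, averaged over the three time points, with "3 repeated measurements having a AR(1) covariance structure, SD=2, ICC=0.2 and 0.05 alpha".

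On retention, 10.4 says: "With attrition conservatively estimated at 20% we expect a final sample size of 128". That is 64 per group under equal allocation, which is an assumption because the ratio is not given. Sidedness is not stated. Averaging over time points is stated for pain intensity but not for disability.

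**The concern.** The two calculations share the number of assessments, the correlation structure, the correlation and alpha, so they can be compared directly.

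- A disability difference of 1.0 with SD 4 is 0.25 SD. The pain difference of 0.75 with SD 2 is 0.375 SD. At nearly equal group sizes the smaller standardised effect is credited with the higher power, 84% against 80%.
- A disability difference of 1.5 with SD 4 is also 0.375 SD, identical to the pain effect. Yet three more participants per group are said to lift power from 80% to 99%.

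The sample-size argument for the Section 3.1 primary endpoint rests on the disability line. If SD 4 is the right input, the trial has roughly even odds of detecting the difference it names. A reader who trusted the 84% would take a null result as much stronger evidence against a 1.0-point effect than it is.

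**Working it through.** **Inputs, all from 10.4:** 3 assessments; AR(1) with correlation 0.2; alpha 0.05, taken as two-sided. Disability: n = 52 per group, SD 4, differences 1.0 and 1.5. Pain: n = 49 per group, SD 2, difference 0.75.

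**Formula.** For the average of three AR(1) measurements the variance factor is

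f = [3 + 2(2 × 0.2 + 0.2²)] / 9 = 3.88 / 9 = 0.4311.

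The standard error of the group difference is SE = SD × √(2f/n), and power = Φ(difference/SE − 1.96).

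**Step 1: the plan's pain-intensity figure.**
SE = 2 × √(0.4311 × 2/49) = 0.265; 0.75/0.265 = 2.83; power = Φ(0.87) = 80.7% (79.9% with the noncentral t). The sample size for 80% is exactly 49 per group. The stated figure reproduces.

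**Step 2: the disability figures with the same formula.**
SE = 4 × √(0.4311 × 2/52) = 0.515.

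- Difference 1.0: 1.0/0.515 = 1.94; power = Φ(−0.02) = 49.3% (t-based 48.5%). Stated: 84%.
- Difference 1.5: 1.5/0.515 = 2.91; power = Φ(0.95) = 83.0% (t-based 82.2%). Stated: 99%.

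Generalised least squares weighting of the three assessments has factor 0.4286 and SE 0.514. It changes the results only to 49.5% and 83.2%.

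**Step 3: other readings at SD 4.**

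| Reading | Difference 1.0 | Difference 1.5 |
|---|---|---|
| Stated in plan | 84% | 99% |
| One-sided, 52 per group | 62% | 90% |
| Compound symmetry, 52 per group | 46% | 80% |
| Zero correlation, 52 per group | 60% | 91% |
| Zero correlation and one-sided, 52 per group | 71% | 95% |
| Single time point, 52 per group | 25% | 48% |
| Two-sided AR(1), 64 per group (128 completers) | 58% | 90% |
| Two-sided AR(1), 80 per group (160, no attrition) | 67% | 95% |
| Two-sided AR(1), 104 per group | 78% | 98% |

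None recovers the stated pair. Reading the 4 as a variance (SD 2) overshoots, at 97% for a difference of 1.0.

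**Step 4: what the stated figures would require.**

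- At SD 4 and 52 per group, the difference detectable with 84% power is 1.52, and with 99% power about 2.2.
- At SD 4, 84% power for a difference of 1.0 needs (1.96 + 0.994)² × 2 × 16 × 0.4311 ≈ 120.4, so 121 per group.
- At 52 per group, 84% for a difference of 1.0 implies an SD of 2.63. That SD also gives 99.3% for 1.5, so one SD explains both stated figures. It equals 4 × √0.4311 = 2.63, as if the reduction for repeated measures had been applied twice. That explanation is an inference from the numbers; the protocol does not say so.

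**The case against.** The arithmetic is hard to contest, but several points can be made about what follows from it.

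- **SD 4 may be the error.** The stated pair is mutually consistent at an SD of about 2.63, so the powers could be right and the SD misprinted. This stands: the low power is conditional on SD 4. It does not remove the error, because the text is wrong either way.
- **The sample size has other supports.** Section 10.4 also cites prior experience, the available pool of candidates and the pain calculation, which reproduces and reaches about 90% at 64 per group. This stands, but Section 3.1 makes pain reduction secondary.
- **Disability is not consistently the sole primary.** Section 1.2 also lists coping and pain among the primary outcomes, and Table 5 lists the daily diary and the coping questionnaire. True, but disability is primary or part of a primary measure in each place.
- **It is a pilot.** A null result would be judged by its estimate and interval as well as by planned power. That tempers the consequence, but the plan makes an explicit power claim and Section 1.2 predicts significant between-group benefit.
- **The disability estimand and sidedness are unstated.** The defensible claim is that no tested reading with three assessments reproduces the figures. Treating the seven diary days as seven AR(1) measurements gives 81% and 99%, which is close, but it contradicts the three assessments stated and still misses 84%.

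**Conclusion.** The concern holds. On the inputs in 10.4, power for pain-related disability is about 49% for a difference of 1.0 (84% stated) and about 83% for 1.5 (99% stated). At the expected 64 completers per group it is about 58% and 90%. These results assume a two-sided test, averaging over the three assessments and, for the 64, equal allocation. The finding that the stated powers are wrong for the stated inputs does not depend on those choices: even a one-sided test with zero correlation gives 71% for a difference of 1.0. What the documents cannot settle is whether the SD or the powers are misprinted. The practical consequence, near-even odds of detecting 1.0, applies if SD 4 is correct.

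The time-averaged reading is also a generous one. Section 14.1 plans group-by-time contrasts of change from pre-treatment. For the change from T1 to T2 the variance factor is 2(1 − 0.2) = 1.6, and at 52 per group power is 17% for a difference of 1.0 and 33% for 1.5.

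**What to change.** Correct 10.4 in one of two ways, after the sponsor checks the original calculation:

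1. **If SD 4 is right,** replace the stated powers. With 64 completers per group, AR(1) with correlation 0.2 and a two-sided time-averaged test, power is about 58% for a difference of 1.0 and 90% for 1.5.
2. **If SD 4 is a misprint,** give the correct SD with its source. About 2.63 is the value the stated powers imply.

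In either case, state the sidedness, the disability estimand (average over assessments or change from baseline) and whether the SD refers to daily scores or a weekly mean, so that the figure can be reproduced and matched to the analysis in 14.1.

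The cost is a text amendment. Enrolment need not change to make the statement true; under the first option the stated power simply becomes less favourable. Keeping 84% power for a difference of 1.0 at SD 4 would be a different decision: about 121 completers per group, or 242/0.8 ≈ 303 enrolled at the plan's 20% attrition, against the planned 160.

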Both groups will complete baseline (T1) measures online prior to randomization. Participants will be randomly allocated to either the experimental (*iCanCope with Sickle Cell Pain*) or attention control education group. Following program completion at 2 months (T2), participants will be asked to complete post-test measures. Electronic and SMS text reminders will also be sent by the study team. Participants will be asked to complete the same measures at 6 months (T3) following completion of the intervention or control condition. All measures will be completed online, either at home or in clinic. Paper versions of measures will be available if online access is not possible. Participants in both groups will be able to contact staff for technical problems with the app or website. Research staff will also be available at routine clinic visits during the study period.

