### **Analytic plan for Aim 1**

Feasibility will be determined by calculating rates of accrual, drop out, compliance, and missing data with 95% CI's. Criteria for feasibility success will be based on previous studies by our group: accrual rates >70%, attrition rates <20%, minimal technical difficulties (i.e., reported by <10%), high acceptability and satisfaction (item mean score of 4 on AES), adherence rates >80%, and minimal missed responses. In Aim 1, we will also determine preliminary efficacy of the intervention. To account for clustering due to repeated assessments within individuals, generalized estimating equations (GEE) will be used. Interaction terms will be used to compare the mean change from pre-treatment to post-treatment for the *iCanCope* group with the corresponding mean change for the *Attention Control Education* group. Single degree of freedom contrasts will test if there is a statistically significant change in pain and coping from pre-treatment to immediate post-treatment for the two groups separately; additional contrasts will be computed to test if there is a statistically significant mean change from baseline to the 6-month follow-up for each group. Secondary treatment outcomes (physical and emotional function, HRQL) will also be examined using GEE to test significant mean changes over time and between groups by using interaction terms and contrasts. Treatment fidelity will be assessed by examining differential attrition (completers vs. non-completers) between and within groups using chi-squared tests and logistic regression models.

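### The 80% power stated for pain intensity is that of a three-point average including the pre-randomisation baseline; the planned interaction test has about 39% or 71%, depending on what 0.75 means

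*Combined protocol and SAP*

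**What the plan says.** Section 10.4 plans 160 participants, allows for 20% attrition and expects 128, which is 64 per arm. For pain intensity it states that "group sample sizes of 49 and 49 achieve 80% power to detect a difference of 0.75 in pain intensity (average over three time points", with "AR(1) covariance structure, SD=2, ICC=0.2 and 0.05 alpha".

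Sections 5.1 and 5.4 define exactly three assessments: T1 before treatment, T2 after treatment at 2 months, and T3 at 6 months after the intervention. Section 5.2, under Both Groups, has participants complete the T1 "measures online prior to randomization".

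The Aim 1 analysis in section 14.1 uses GEE. Its between-arm test is given as "Interaction terms will be used to compare the mean change from pre-treatment to post-treatment" in one group against the other. The further contrasts it describes for pain and coping are changes within each group, to T2 and to T3. Section 14.1 does not describe a test of an average over the three assessments, and section 10.4 gives no power for the interaction.

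The documents differ on the rank of pain: section 1.2 and Table 5 treat it as a primary outcome, section 3.1 as secondary. Section 10.4 claims power for it either way.

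**The concern.** A power statement describes one test of one effect. Here the effect is a difference averaged over three assessments, one of which precedes randomisation, so its expected between-arm difference is zero. The test that the plan names is a difference in change from baseline.

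The two respond in opposite ways to the assumed correlation. A low correlation between assessments makes an average more precise and a change score less precise. An input of 0.2 therefore favours the stated calculation and works against the planned test.

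At stake is what the trial can say about pain. If the planned test has much less than 80% power, readers who rely on section 10.4 will misjudge how informative a non-significant interaction would be.

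**Working it through.** **Inputs (section 10.4).** SD 2; AR(1) with lag-1 correlation r = 0.2 (labelled ICC), so the T1–T3 correlation is 0.04; difference 0.75; alpha 0.05; 49 per arm in the calculation, 64 per arm expected. Sidedness is not stated. Two-sided is assumed, because it reproduces the stated figure while one-sided gives 88%.

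**Formula.** For a contrast with per-person variance V, SE = √(2V/n), z = difference/SE, and power ≈ Φ(z − 1.96).

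**1. Reproducing the 80%.** Mean of T1, T2 and T3: V = (SD²/9)(3 + 2(2r + r²)) = (4/9)(3.88) = 1.724. With n = 49, SE = 0.265, z = 2.83 and power is 80.7%. The alternatives tried at n = 49 do not give 80%: compound symmetry 77.6%, mean of T2 and T3 only 66.9%, a single time point 45.9%.

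**2. The planned test.** Change from T1 to T2: V = 2·SD²·(1 − r) = 2 × 4 × 0.8 = 6.4. With n = 64, SE = √(12.8/64) = 0.447.

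- *Reading A: 0.75 is the between-arm difference in change.* z = 0.75/0.447 = 1.68, power 38.9%. A simulation gave 39.3%. At 49 per arm it is 31.1%, and at 80 per arm (no attrition) 46.6%.
- *Reading B: 0.75 is the three-point average, with zero at T1 and equal effects at T2 and T3.* The post-treatment difference is 0.75 × 3/2 = 1.125. z = 1.125/0.447 = 2.52, power 71.1%. At 80 per arm it is 80.3%.

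**3. Sensitivity to the correlation (64 per arm, other T1–T2 correlations assumed).**

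| Correlation | V of change | Power, reading A |
|---|---|---|
| 0.2 (plan) | 6.4 | 39% |
| 0.3 | 5.6 | 43% |
| 0.5 | 4.0 | 56% |
| 0.7 | 2.4 | 78% |

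Under reading B, a correlation of 0.5 would give z = 1.125/0.354 = 3.18 and power of 89%. The same correlation would lower the stated three-point figure at 49 per arm from 80.7% to 66%, so section 10.4 would need restating in that case too.

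**4. Detectable difference.** At 80% power with 64 per arm: (1.96 + 0.84) × 0.447 ≈ 1.25 points of change.

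**5. Effect of including the baseline.** A true 0.75 at both T2 and T3, with zero at T1, averages 0.5 over three points. The three-point test then has 47.0% power at 49 per arm and 57.7% at 64.

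**6. A baseline-adjusted mean of T2 and T3.** Variance of the mean: (4/4)(2 + 2 × 0.2) = 2.4. Covariance with T1: 4 × (0.2 + 0.04)/2 = 0.48. Residual variance: 2.4 − 0.48²/4 = 2.342. For 0.75 with n = 64, SE = 0.271, z = 2.77 and power is 79.2%. At 49 per arm it is 67.9%.

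**The case against.** The strongest reply is that section 10.4 defines 0.75 as a three-point average, so moving it onto change changes the effect as well as the test. That stands. A reader might infer that the planned test simply has 39% power, but the documents do not fix that reading. Taken literally, with nothing at T1, the figure is 71%. Section 10.4 does not say that it assumes a post-treatment difference of 1.125, so neither reading can be excluded.

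The correlation of 0.2 is also given without a source or a time lag, and change-score power depends heavily on it. This calls for a range, not for dismissing the point.

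A reader might infer an arithmetic slip. The 80% reproduces, so that is not supported. A reader might also infer that the trial is too small and needs the 179 per arm that reading A would require. That does not follow either: the stated three-point test has about 90% power at 64 per arm, and a baseline-adjusted comparison of 0.75 over T2 and T3 has 79%. The sample is close to adequate for a sensible post-treatment contrast. If partial data from all randomised participants contribute, 64 per arm may also understate the information.

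Finally, this is called a pilot, its aims include feasibility, and section 3.1 ranks pain as secondary. That lowers the stakes. But section 10.4 rests the sample size on this calculation, and section 1.2 hypothesises a significant pain reduction against control as a primary outcome. Nothing in the documents says how a null pain result will be interpreted, so over-reading it is a risk, not a stated intention.

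**Conclusion.** The point holds as a mismatch between the sample-size basis and the analysis. Section 10.4 gives the power of a comparison that section 14.1 does not plan, on an average diluted by a pre-randomisation measurement.

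With the plan's SD and correlation, two-sided 0.05 and 64 per arm, the planned T1-to-T2 interaction has about 39% power (0.75 as difference in change) or about 71% (0.75 as three-point average). Under the first reading it stays below 80% up to an assumed correlation of 0.7. Only departures from the plan's own inputs lift the second reading to 80% or more: no attrition at all (80.3%), or a higher correlation. The calculations assume complete data on the participants counted and equal effects at T2 and T3 where an average is used.

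**What to change.** Keep enrolment at 160. Before outcome data are examined, do one of the following.

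- **(a) Restate the pain power in section 10.4 for the interaction actually tested.** Say whether 0.75 is a difference in change or a three-point average, give the power at 64 per arm (39% or 71%) and the detectable difference in change (about 1.25 points), and show the sensitivity to the correlation.
- **(b) Pre-specify the between-arm pain analysis in section 14.1 as a baseline-adjusted comparison averaged over T2 and T3, and base section 10.4 on it.** This has about 79% power for 0.75 at 64 per arm with the same inputs, and uses only assessments already scheduled.

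Option (a) costs a less favourable stated power. Option (b) costs a documented amendment to the pain contrast, dated before outcomes are seen, and the text should also settle whether pain is primary or secondary. Neither changes data collection.

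The disability figures in the same paragraph should be checked in the same revision. The three-point method that reproduces the pain figure gives 49% and 83% there, against the stated 84% and 99%.

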**11.2. Procedures for orderly termination:**

If a participant must be withdrawn from all study procedures the study staff would contact the family to explain the cause for study withdrawal and finalized study termination.

**11.3. Procedures that will be followed when subjects withdraw from the research, including partial withdrawal from procedures with continued data collection and withdrawal from data/specimen banking:**

Full Withdrawal: If a participant must be withdrawn from all study procedures the study staff would contact the family to explain the cause for study withdrawal and finalized study termination.

Partial Withdrawal: If a participant partially withdraws from the procedures, study staff would contact the family to discuss family's interest in participation. If the family is interested, the study procedures will be continued, if the family is not interested, this will be considered a full withdrawal.

**12. Risks to Subjects****12.1. Reasonably foreseeable risks to subjects (include each study population, each arm, and optional procedures):**

This study is minimal risk. There are potential risks around emotional distress, time commitment, and confidentiality. Although asking about physical symptoms and mood/behavior does not typically result in any distress, there is a small risk of emotional

distress. There is a potential risk of loss of confidentiality. Some of the questionnaires include questions that could uncover depression or suicidal ideation. See below for plan.

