**14. Data Analysis/Management**

**14.1. Data analysis plan, including statistical procedures:**

Data analyses will be performed using SPSS v20.0 and SAS v9.3. Distributions of primary and secondary outcome variables at each time point (and on difference scores between time points) will be examined first with summary statistics and graphical tools. For outcome variables with highly skewed distributions, we will either apply transformation or non-parametric test procedures. Preliminary work will also involve computation of scale reliabilities (e.g., internal consistency using Cronbach's alpha) of all of the self-report measures. The pilot RCT analysis will be an intent-to-treat analysis including all randomized subjects.

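### Section 11 lets the PI withdraw families who cannot comply and gives no route for still collecting T2 and T3 outcomes

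*Combined protocol and SAP*

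**What the plan says.** Section 11.1, on withdrawal without the subject's consent: "The PI may decide to withdraw participants from the study if a family is not able to comply with study procedures". Failure to understand the instructions is a second ground. No criteria or threshold are given.

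Sections 11.2 and 11.3, on families who leave the study entirely, read as follows: "If a participant must be withdrawn from all study procedures the study staff would contact the family to explain the cause for study withdrawal", after which termination is finalised. No later assessment is mentioned.

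Section 11.3, on partial withdrawal: staff ask about the family's interest in taking part. There are two branches. The first is "If the family is interested, the study procedures will be continued". The second is "if the family is not interested, this will be considered a full withdrawal". The heading of 11.3 refers to people who leave some procedures while data are still collected, but the text beneath does not describe that arrangement.

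Section 14.1: "The pilot RCT analysis will be an intent-to-treat analysis including all randomized subjects". For Aim 1, "generalized estimating equations (GEE) will be used", with interaction terms and contrasts for change from baseline to T2 and to T3. Losses are addressed by "examining differential attrition (completers vs. non-completers) between and within groups", under the label of treatment fidelity. No imputation, weighting or sensitivity analysis for missing outcomes is stated. The feasibility criteria include adherence above 80% and attrition below 20%. Neither denominator is defined.

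**The concern.** Intent-to-treat depends on following everyone randomised, whatever they did with the programme. Baseline is completed before randomisation, so any withdrawal during the programme or follow-up is a post-randomisation event. If it is triggered by compliance, the youth whose outcomes are lost are selected on something plausibly related to how they fare.

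The point matters more here because compliance is itself under study. Adherence and attrition are feasibility criteria, and engagement is an Aim 3 moderator, so losing outcomes in the least compliant families narrows the range over which that moderator can be examined. Low use is foreseeable: the background section reports an earlier smartphone programme in this disease in which coping skills were opened on only 12% of days. Outcomes that were never requested cannot be recovered at analysis.

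**Working it through.** **1. The plan's own figure.** Section 10.4 enrols 160 and expects 20% attrition: 160 × (1 − 0.20) = 128, which reproduces. With equal allocation (assumed; the power calculation uses equal groups) that is 80 randomised and 64 retained per arm.

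For pain intensity, the SD of the mean of three AR(1) measurements with SD 2 and correlation 0.2 is 2 × √(3 + 4 × 0.2 + 2 × 0.2²)/3 = 2 × √3.88/3 = 1.313. A difference of 0.75, two-sided alpha 0.05 (sidedness is not stated), gives power of 80.7% at 49 per arm, against the stated 80%, and 89.8% at 64 per arm. So for this outcome the issue is which youth are missing rather than how many.

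**2. What section 11 does in four cases.**
- The PI uses 11.1. The family leaves the study, and the only described consequence is termination. Whether T2 and T3 are still requested is not said.
- A family stops the programme but would answer questionnaires. Under 11.3 it may count as interested, in which case procedures continue, but the text does not say that questionnaires alone would be enough. If it counts as not interested, it is fully withdrawn.
- A family declines everything. Collection ends by its own choice, which is proper.
- A youth is withdrawn after T2. The T2 data exist and only T3 is at risk.

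The gap lies in the first two cases.

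**3. What this does to the analysis.** A youth with baseline data only stays in the analysis set but carries no information on change to T2 or T3. Unweighted GEE is in general valid only if missingness is unrelated to the outcomes given the model's covariates. Withdrawal for failing to comply is unlikely to meet that condition, and the plan states no alternative. Comparing completers with non-completers describes the loss but does not correct for it.

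**4. Illustration of size.** None of these shares is in the documents. Let a share w of the iCanCope arm be lost through this rule, gain no benefit, and have the same prognosis as the rest. If the effect in those who remain is δ, the all-randomised effect is (1 − w)δ, and the available-case estimate overstates it by the factor 1/(1 − w). The last column takes the plan's pain difference of 0.75 as the available-case result.

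| w | Youth of 80 | 1/(1 − w) | All-randomised effect |
|---|---|---|---|
| 5% | 4 | 1/0.95 = 1.05 | 0.75 × 0.95 = 0.71 |
| 15% | 12 | 1/0.85 = 1.18 | 0.75 × 0.85 = 0.64 |
| 20% | 16 | 1/0.80 = 1.25 | 0.75 × 0.80 = 0.60 |

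Planned attrition from all causes is 20%, so the 15% row gives three-quarters of it to this rule in one arm, and the 20% row gives it all. Those rows are high cases.

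**5. If prognosis differs instead.** Suppose there is no treatment effect and lost youth would have scored g points worse than the rest. The bias is (w₁ − w₀) × g, where w₁ and w₀ are the shares lost in the two arms. Equal loss of 20% gives 0. Loss of 25% against 15% with g = 1 point gives 0.10 × 1 = 0.10 points in favour of iCanCope. The bias therefore turns on a difference between arms that cannot be known in advance.

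**The case against.** The strongest reply is that section 11 is short template text and is milder than it looks. The power is discretionary and concerns inability to comply, not low use. Elsewhere the protocol expects variable use: it tracks usage in both arms, allows up to 12 weeks, and pays for each completed assessment without reference to programme use. All of this stands, and it rules out four stronger readings.

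- A reader might infer that youth who do not engage are automatically withdrawn. No section says so.
- A reader might infer that any family that stops the programme is classed as fully withdrawn. The first branch of 11.3 continues procedures for an interested family, and a family willing to answer questionnaires could fit it.
- A reader might infer a contradiction with intent-to-treat. No section removes withdrawn youth from the analysis set, and their available data can enter the GEE.
- A reader might infer that discretionary withdrawals could carry the trial past its adherence criterion. For example, dropping 10% with zero adherence from a mean of 75% (the Web-MAP pilot's 6 of 8 modules) gives 0.75/0.90 = 83%. That needs withdrawn youth to leave the denominator, which the plan does not say. It also assumes that adherence means modules completed, which is undefined, and borrows a figure from 12 users of a different programme. PI withdrawals would most naturally count as attrition and so make that criterion harder to meet.

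Nor do the documents show that loss will be greater in the iCanCope arm. Its programme asks more of families, but control families also have six sections and four check-in contacts, and the plan will test differential attrition.

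The reply leaves one thing unanswered: after a PI-initiated withdrawal, or when a family leaves only the programme, the protocol does not provide for T2 and T3.

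**Conclusion.** The point holds as a cheap improvement. Section 11 permits withdrawal from the study for inability to comply, describes full withdrawal as the end of all procedures, and offers no assessments-only route. Following it can create avoidable, compliance-related missing outcomes in a trial that promises to analyse everyone randomised and states no missing-data method. This undercuts the intent-to-treat aim; it is not a formal contradiction and not a demonstrated bias.

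The conclusion rests on reading an end to outcome collection into the termination wording. How often the power would be used, and whether use would differ by arm, is unknown. The overstatement of 5% to 25% is conditional on the assumed shares, on no benefit in those lost, and on equal prognosis.

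**What to change.** Amend 11.1 and 11.3 so that non-compliance with the programme, or leaving it, does not by itself end outcome assessment. Keep requesting T2 and T3 unless the family withdraws from data collection, and record which kind of withdrawal occurred and who initiated it. In section 14.1, state that all randomised youth, including those withdrawn by the PI, count in the adherence and attrition denominators.

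The cost is protocol wording, some further reminders and gift cards. Measures are online and can be done at home. At $40 per dyad per assessment, two assessments cost $80, so 4 to 16 dyads (5% to 20% of an arm of 80) would cost $320 to $1,280. A family that declines further contact for data collection is left alone, as now.
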